ADE	Adverse device effect - Adverse event related to the use of an investigational medical device. Note: This definition includes adverse events resulting from insufficient or inadequate instructions for use, deployment, implantation, installation, or operation or any malfunction of the investigational medical device. Note: This definition includes any event resulting from use error or from intentional misuse of the investigational medical device. See Clinical Event definition for more information.
AE	Adverse event - Any untoward medical occurrence, unintended disease or injury, or untoward clinical signs (including abnormal laboratory findings) in subjects, users or other persons, whether or not related to the investigational medical device. Note: This definition includes events related to the investigational medical device or the comparator. Note: This definition includes events related to the procedures involved. Note: for users or other persons, this definition is restricted to events related to investigational medical devices. See Clinical Event definition for more information.
ASA	American Society of Anesthesiologists
ВМІ	Body mass index (kg/m²) - BMI is a person's weight in kilograms (kg) divided by his or her height in meters squared.
СС	Cubic centimeter (liquid volume)
CIP	Clinical Investigation Plan (can be used synonymously with Protocol)

MDT17025SIG Version 3.0 Page 8 of 57

[figure not shown]
Term	Definition
COPD	Chronic obstructive pulmonary disease - a chronic condition in which there is a slow, progressive obstruction of airflow into or out of the lungs
Device Deficiency	Inadequacy of a medical device with respect to its identity, quality, durability, reliability, safety or performance. Note: Device deficiencies include malfunctions, use errors, and inadequate labeling. See Clinical Event definition for more information.
eCRF	Electronic Case Report Form
ICJME	International Committee of Medical Journal Editors
IFU	Instructions for use
ISO	International Organization for Standardization
ІТТ	Intent-to-treat
LCD	Liquid crystal display
LED	Light emitting diode
LRYGB	Laparoscopic Roux-en-Y gastric bypass — A type of weight loss surgery that reduces the size of the upper stomach to a small pouch by stapling off the upper section of the stomach then attaches this pouch directly to part of the small intestine called the Roux limb forming a "Y" shape.
LSG	Laparoscopic sleeve gastrectomy – A laparoscopic surgical weight-loss procedure in which the stomach is reduced, by surgical removal of a large portion of the stomach along the greater curvature resulting in a sleeve or tube-like structure
MedDRA	Medical Dictionary for Regulatory Activities

MDT17025SIG Version 3.0 Page 9 of 57

Term	Definition			
OLED	Organic light emitting diodes			
RDC	Remote data capture			
SAE	Serious Adverse Event - Adverse event that: a. Led to a death, b. Led to a serious deterioration in the health of the subject, that either resulted in: 1. Resulted in a life threatening illness or injury, or 2. Resulted in a permanent impairment of a body structure or a body function, or 3. In-patient or prolonged hospitalization, or 4. Medical or surgical intervention to prevent life threatening illness or injury or permanent impairment to a body structure or a body function, or c. Led to fetal distress, fetal death or a congenital abnormality or birth defect. Note: Planned hospitalization for a pre-existing condition, or a procedure required by the CIP, without serious deterioration in health, is not considered a serious adverse event.			
SADE	Serious Adverse Device Effect - Adverse device effect that has resulted in any of the consequences characteristic of a serious adverse event.			
USADE	Unanticipated Serious Adverse Device Effect - Any serious adverse device effect which by its nature, incidence, severity or outcome has not been identified in the current version of the risk analysis report. Note: Anticipated serious adverse device effect (ASADE) is an effect which by nature, incidence, severity or outcome has been identified in the risk analysis report.			
VATS	Video assisted thoracic surgery			

MDT17025SIG Version 3.0 Page 10 of 57

3. Synopsis

Title	A prospective two arm multicenter pact market study to confirm				
Title	A prospective, two-arm, multicenter, post market study to confirm				
	the safety and performance of the Signia™ Stapling System using				
	Endo GIA™ Reloads with Tri-Staple™ Technology and Tri-Staple™ 2.0				
	Intelligent Reloads in abdominal and thoracic procedures.				
Clinical Study Type	Post-market, prospective, two-arm, multi-center				
Product Name	Signia™ Stapling System using Endo GIA™ Reloads with Tri-Staple™				
	Technology and Tri-Staple™ 2.0 Intelligent Reloads				
Sponsor	Covidien-Medtronic				
	Minimally Invasive Therapies Group				
	Surgical Innovations				
	[name]				
	[name]				
Local Sponsor	Covidien Services Europe (an indirect, wholly owned subsidiary of				
	Medtronic plc.)				
	Medtronic PLC,				
	[name],				
	[name]				
Indication under	Abdominal and thoracic procedures for resection, transection and				
investigation	creation of anastomosis per the instructions for use (IFU)				
Product Status	Signia™ Stapling System				
	 Food and Drug Administration (FDA) 510K cleared (USA) 				
	 CE Mark approval (EU), Self-Declared 				
Primary Objective(s)	The objectives of this prospective, two-arm, multicenter post-market				
	study is to confirm safety and performance through the incidence of				
	subjects reporting serious adverse device effects (ADEs) up to and				
	including 30 (+14) days following use of Signia™ Stapling System with				
	Endo GIA™ with Tri-Staple™ Technology and Tri-Staple™ 2.0				
	Intelligent Reloads in subjects undergoing indicated abdominal or				
	thoracic procedures for resection, transection and creation of				
	anastomosis per the IFU.				
Secondary Objective(s)	The secondary endpoint is device deficiency/malfunctions affecting				
	the intended performance of the device to include;				

MDT17025SIG Version 3.0 Page 11 of 57

	Charle Parameters					
	Staple line assessment:					
	o Intraoperative assessments:					
	 Assessment of staple line integrity 					
	 Incidence of staple line bleeding (measured as ≥ 50 cc) 					
	Additional intervention(s) to treat staple-line					
	failure (ex: glue, manual over sew, Medtronic					
	buttress) or intraoperative					
	revision/recreation of the anastomosis					
	 Incidence of leakage (as measured by air leak 					
	test, or standard of care, as applicable)					
	 Post-operative assessments: 					
	 Duration of air leakage (in days) for thoracic 					
	procedures					
	 Prolonged air leaks are considered >7 days 					
	Incidence of leakage for abdominal					
	procedures as evidenced confirmed by					
	imaging, subject presentation or decline in					
	status, or need for reoperation/re-					
	intervention					
	 Incidence of post-operative infection 					
	assessed by the Investigator according to the					
	standard of care and site policy, ex. Positive					
	wound culture					
	 Additional intervention(s) to treat staple-line failure 					
	 Incidence of repeat hospital admissions for primary procedure-related complications. 					
	All recorded device deficiencies/malfunctions will be captured and					
	assessed by the Investigator. Complaints will be handled in					
	accordance with the standard procedures for the post-market					
	vigilance system.					
Randomization	There will be no randomization used for this study					
Sample Size	A minimum of 127 subjects will be enrolled under 2 study arms,					
	(abdominal or thoracic) at approximately 10 sites in the USA and					
	Europe (potentially in United Kingdom, Spain, Italy).					
	 Abdominal (approximately 53 subjects) 					
	 Thoracic (approximately 74 subjects) 					
Inclusion/Exclusion Criteria	Inclusion Criteria					

MDT17025SIG Version 3.0 Page 12 of 57

- 1. Adults (male or female) between 22 and 80 years of age inclusive at the time of the procedure.
- 2. The subject must be willing and able to participate in the study procedures and to understand and sign the informed consent.
- 3. The subject is scheduled to undergo an indicated primary abdominal or thoracic procedure for resection, transection and creation of anastomosis per the IFU where the Signia™ Stapling System with Endo GIA™ with Tri-Staple™ Technology and Tri-Staple™ 2.0 Intelligent Reloads will be used per its IFU. Additionally, if considered appropriate for the procedure only Medtronic buttresses can be used during the course of the study.
 - a. Thoracic procedures may include, but are not limited to wedge resection and lobectomy, and may include video assisted thoracic surgery (VATS) or open procedures
 - b. Abdominal procedures may include, but are not limited to, laparoscopic sleeve gastrectomy (LSG), laparoscopic Roux-en-Y gastric bypass (LRYGB)

Exclusion Criteria

- 1. Subjects undergoing cardiac and vascular procedures
- 2. The procedure is an emergency procedure
- 3. The procedure is a revision/reoperation of a primary operation
- 4. Any female subject who is pregnant
 - a. Females of child-bearing potential will be required to undergo either a urine pregnancy test or serum pregnancy test during Screening and confirmed on the day of operation (except for subjects who are surgically sterile or are post-menopausal for at least two years) (USA only) and per EU local requirements
- 5. Any subject who is considered to be part of a vulnerable population (e.g. prisoners or those without sufficient mental capacity)
- 6. The subject is unable or unwilling to comply with the study requirements or follow-up schedule
- 7. The subject has comorbidities which, in the clinical judgment of the Investigator, will not be appropriate for the study or the subject has an estimated life expectancy of less than 6 months
- 8. The subject has been diagnosed with a bleeding disorder and/or is undergoing active and not reversed anticoagulant treatment.

MDT17025SIG Version 3.0 Page 13 of 57

	9. The subject is concurrently enrolled in another investigational
Study Procedures and Assessments	drug or device research study or has been enrolled in another study within 30 days of enrollment. 10. Pre-existing/chronic conditions specific to Tri-Staple™ 2.0 Reload contraindications as described in the IFU. Subjects will be evaluated at screening, day of operative visit, discharge, and 30 (+14) days post-operative. Assessments to be conducted/data collected include:
	 Screening: Eligibility Criteria Subject demographics (e.g., sex, age, ethnicity and race if allowed per local regulations) Medical and surgical history (previous abdominal or thoracic surgical history, smoking history, anticoagulant therapies and prevalence of diabetes) Vital signs (heart rate, temperature, respiratory rate, blood pressure) Oxygen saturation levels BMI Abbreviated physical exam, including height, weight, and examination of the heart, lung, and abdomen Serum or urine pregnancy test females of child bearing potential (USA only) or per EU local requirements Operative Visit:

MDT17025SIG Version 3.0 Page 14 of 57

[figure not shown]

- Eligibility Criteria*
- Vital signs (heart rate, temperature, respiratory rate, blood pressure, pulse, oxygen saturation levels)*
- Abbreviated physical exam, including height, weight, and examination of the heart, lung, and abdomen*
- American Society of Anesthesiologists (ASA) grade (See Appendix B, Section 18.2)
- Serum or urine pregnancy test females of child bearing potential (USA only) or per EU local requirements *
- * Assessments only need to be repeated if Screening/Operative Visit occur on different days
 - Operative date
 - Operative start (skin incision) and stop times (skin closure)
 - Type of procedure
 - General anesthesia information (type, start and stop times)
 - Study device data (i.e., type of reload used, staple size, lot number of devices used, number of firings, location of firings)
 - Use of Signia feedback display during surgery (if applicable)
 - Relevant concomitant medications (only those related to relevant medical history or adverse events will be collected e.g.: anticoagulants, blood pressure, antibiotics, pain medications)
 - Procedure related adverse events and adverse device effects (ADEs)
 - Staple line assessment
 - Device deficiencies/malfunctions affecting intended performance to include but not limited to;
 - System set-up (insertion guide, power shell)
 - Organic light emitting diode (OLED) screen display
 - Rotation
 - o Articulation
 - Clamp/UnClamp
 - Firing
 - o Use of manual retraction tool
 - User errors
 - Unintended cutting
 - Insufficient staple deployment
 - o Inability to complete the firing sequence
 - Stapling without cutting
 - Device accountability

Discharge Assessments:

• Procedure related adverse events and adverse device effects

MDT17025SIG Version 3.0 Page 15 of 57

- Length of hospital stay
- Length of intensive care unit stay (if applicable)
- Surgical site and infection assessment by the Investigator according to the standard of care and site policy, ex. Positive wound culture
- Relevant concomitant medications (only those related to relevant medical history or adverse events will be collected e.g.: anticoagulants, blood pressure, antibiotics, pain medications)

Follow-up Assessments (Post-operative day 30 (+14)):

- Readmission related to primary procedure
- Procedure related adverse events
- Adverse device effects (ADEs)
- Surgical site and infection assessment by the Investigator according to their the standard of care and site policy, ex.
 Positive wound culture
- Relevant concomitant medications (only those related to relevant medical history or adverse events will be collected e.g.: anticoagulants, blood pressure, antibiotics, pain medications)

Statistics

Sample Size Determination

Sample size was determined based on the primary endpoint (incidence of subjects reporting serious adverse device effects up to and including 30 days(+14 days) post-procedure) and considering an acceptable probability (≥ 80%) to observe at least one adverse device effect within 30 days, in each arm (abdominal or thoracic indication).

A previous Medtronic study (ClinicalTrials.gov ID NCT02500537) conducted on N=100 subjects and evaluating an equivalent device (Endo GIA™ Reinforced Reload with Tri-Staple™ Technology) in the same indications and with a similar design and follow-up reported the following adverse device effect rates (described as "device related adverse events" with the study protocol and final report):

	Abdominal	Thoracic
Adverse device effect incidence	3.3%	2.5%

Because of the expected low adverse device effect incidence rate (<5%) in the Abdominal or Thoracic procedures, as described above, a

Medtronic Confidential

Poisson distribution is applied to estimate the probability of observing AE event(s).

In the Abdominal indication, for an anticipated sample size of 53 subjects using an adverse device effect rate of 3.3%, and including a 5% attrition rate within 30 days, we obtain a probability of 81% to observe at least 1 adverse device effect.

In the Thoracic indication, for an anticipated sample size of 74 subjects using an adverse device effect rate of 2.5%, and including a 5% attrition rate within 30 days, we obtain a probability of 83% to observe at least 1 adverse device effect.

For the overall population (in both indications), with a sample size of 127 subjects considering an averaged adverse device effect rate of 2.9% and an attrition rate of 5% within 30 days, we obtain a probability of 97% to observe at least 1 adverse device effect, and a probability of 86% to observe at least 2 adverse device effects.

In any scenario, we will have \geq 80% probability to observe at least 1 adverse device effect in each arm.

Primary Endpoint Analysis

The primary endpoint is the incidence of subjects reporting serious adverse device effects up to and including 30 days (+14 days) postop. It will be summarized using descriptive statistics.

A two-sided 95% confidence interval will also be calculated. The acceptance criteria for this endpoint is an upper limit of the 95% CI below 20%.

The analysis will be performed in abdominal group and in thoracic group, and in the combined groups.

Secondary Endpoint Analysis

The incidence of secondary outcome measures will be summarized using descriptive statistics:

• counts and percentages for categorical data mean, standard deviation, median, minimum and maximum for quantitative data.

Signia [™] Stapling System using Endo GIA [™] Reloads with Tri-Staple [™]				
Technology and Tri-Staple™ 2.0 Intelligent Reloads Clinical				
Investigation Plan				

MDT17025SIG Version 3.0 Page 17 of 57

Medtronic

Interim Analysis	A preliminary analysis will be conducted in the study when a total of
	64 subjects have been enrolled and completed the 30 day follow up
	visits.

4. Introduction

4.1. Background

During abdominal and thoracic procedures, staple line failure can result in severe intraoperative and postoperative complications. After thoracic lung resection, postoperative air leaks are the most common complication with a reported occurrence between 4% and 58% [1-5]. In patients with concomitant chronic obstructive pulmonary disease (COPD) and fused fissures these rates can climb as high as 90% [6]. Thoracic air leak complications can include reduced mobility, increased hospital stay, the need for longer chest tube time (often associated with increased pain), and risk of further complications [1].

With the exception of staple lines across a distal obstruction or severe ileus, leaks are less common during gastrointestinal surgery due to lower intraluminal pressures to which the staple lines are exposed. If leaks do occur; however, the complications can be severe. Postoperative leak rates following laparoscopic sleeve gastrectomy (LSG) and laparoscopic Roux-en-Y gastric bypass (LRYGB) have been reported between 1% and 3% and leak-associated mortality has been reported at 0.1% [7-11].

[figure not shown]
Clearly, the integrity of the staple line is a primary factor in the creation of a stable anastomosis. The various characteristics of each tissue type present unique challenges and until now the firing speed used during these procedures was determined by the surgeon, particularly when using a manual firing setup [12]. Ultimately relying on generation of the ideal 'B' shaped staples, surgeon experience played a crucial role in effective staple line production [13, 12].

The Signia™ Stapling System with Endo GIA™ with Tri-Staple™ Technology and Tri-Staple™ 2.0 Intelligent Reloads uses a single-use reload. Automatically adjusting firing speed to optimize staple formation using an onboard intelligence, the Signia™ Stapling System generates consistent staple lines and real-time surgeon feedback via an OLED display. Additionally, the Signia™ Stapling System can be used single handed. To date single-handed use has proved challenging for many surgeons using manual firing systems.

4.2. Purpose

The purpose of this study is to confirm the safety and performance of the Signia[™] Stapling System with Endo GIA[™] with Tri-Staple[™] Technology and Tri-Staple[™] 2.0 Intelligent Reloads in a minimum of 127 enrolled subjects undergoing indicated abdominal or thoracic procedures enrolled at approximately 10

MDT17025SIG Version 3.0 Page 18 of 57

sites in the USA and Europe (potentially in the United Kingdom, Spain, Italy). At the conclusion of the study, data will be submitted for publication.

5. Objectives and Endpoints

5.1. Objectives

The objective of this prospective, two-arm, multicenter post-market study is to confirm safety and performance through the incidence of subjects reporting serious adverse device effects (ADEs, as defined by ISO14155:2011, see section 11.1.3 for additional details) up to and including 30 (+14) days following use of Signia™ Stapling System with Endo GIA™ with Tri-Staple™ Technology and Tri-Staple™ 2.0 Intelligent Reloads in subjects undergoing indicated abdominal or thoracic procedures. (See Section 18.1 Appendix A, for Reloads to be assessed in this study)

[figure not shown]

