5.1.1. Primary Objective(s)

The primary endpoint is the incidence of subjects reporting serious adverse device effects (ADEs) up to and including the 30 day (+14 day) post-operative follow up visit including intra- and post-operative leaks. The causes of these leaks will be documented when available.

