11.1.6. Device Deficiencies

In alignment with ISO14155:2011 (Section 3.15), a Device deficiency is an inadequacy of a medical device-related to its identity, quality, durability, reliability, safety or performance; such as malfunction, misuse or use error and inadequate labeling.

All Signia™ Stapling System device deficiencies/malfunctions will be documented on the Device Deficiency/Malfunction eCRF.

In the event of a device deficiency the device should be returned to Covidien for analysis, if possible. Instructions for returning the study device will be provided. Device deficiencies should also be documented in the subject's medical record.

Device deficiencies are NOT to be reported as AEs.

However, if there is an AE that results from a device deficiency, that specific event would be recorded on the appropriate eCRF.

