13.4. Statistical Analysis Endpoints

13.4.1. Primary Endpoint

The primary endpoint is the incidence of subjects reporting serious adverse device effects up to and including 30 days (+14days) post-procedure which utilizes the Signia™ Stapling System. It will be summarized using descriptive statistics.

A two-sided 95% confidence interval will also be calculated. The acceptance criteria for this endpoint is an upper limit of the 95% CI below 20%.

The analysis will be performed in abdominal group and in thoracic group, and in the combined groups.

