13.4.2. Secondary Endpoint

The incidence of secondary outcome measures will be summarized using descriptive statistics:

- counts and percentages for categorical data
- mean, standard deviation, median, minimum and maximum for quantitative data.

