The purpose of this study is to confirm the safety and performance of the Signia[™] Stapling System with Endo GIA[™] with Tri-Staple[™] Technology and Tri-Staple[™] 2.0 Intelligent Reloads in a minimum of 127 enrolled subjects undergoing indicated abdominal or thoracic procedures enrolled at approximately 10 sites in the USA and Europe (potentially in the United Kingdom, Spain, Italy). At the conclusion of the study, data will be submitted for publication.

This document outlines the detailed statistical methods to be implemented for the data collected within

the scope of the study. The Clinical Investigation Plan (CIP) document was used to create the Statistical Analysis Plan (SAP).

Version [Final#1.0]

4. Study Objectives

The objective of this prospective, two-arm, multicenter post-market study is to confirm safety and performance through the incidence of subjects reporting serious adverse device effects (ADEs, as defined by ISO14155:2011, see section 11.1.3 for additional details) up to and including 30 (+14) days following use of Signia[™] Stapling System with Endo GIA[™] with Tri-Staple[™] Technology and Tri-Staple[™] 2.0 Intelligent Reloads in subjects undergoing indicated abdominal or thoracic procedures. (See Section 18.1 Appendix A, for Reloads to be assessed in this study)

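### The plan confirms safety and performance through serious adverse device effects and sets its only pass limit there, so its wording could support a performance claim that no malfunction result could overturn

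*Protocol*

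**What the plan says.** Protocol 5.1 states that the objective "is to confirm safety and performance through the incidence of subjects reporting serious adverse device effects". The synopsis repeats this, and SAP 4 has the same link: "performance through the incidence of subjects reporting serious adverse device effects (ADEs, as defined by ISO14155:2011, see section 11.1.3 for additional details".

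Protocol 13.4.1 defines the endpoint for analysis: "The primary endpoint is the incidence of subjects reporting serious adverse device effects up to and including 30 days (+14days"). It then adds: "A two-sided 95% confidence interval will also be calculated", and "The acceptance criteria for this endpoint is an upper limit of the 95% CI below 20"%. The analysis is done by arm and combined. Protocol 5.1.1 describes the same endpoint more widely, up to the "post-operative follow up visit including intra- and post-operative leaks".

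On malfunctions, Protocol 11.1.6 says: "Device deficiencies are NOT to be reported as AEs". An adverse event that results from a deficiency is recorded, and Protocol 11.1.4 makes it a SADE only if it has a serious consequence.

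The secondary endpoint (Protocol 5.1.2, SAP 4.2 and 7.9) is device deficiency or malfunction affecting intended performance, with staple-line outcomes, infection and readmission listed under it. Its analysis (Protocol 13.4.2) is: "The incidence of secondary outcome measures will be summarized using descriptive statistics". Protocol 9.7 says that recorded deficiencies are used to assess efficacy.

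**The concern.** Two claims, safety and performance, are attached to one endpoint, and that endpoint is a harm endpoint. Protocol 9.7.1 lists the failures that bear on performance: incomplete firing sequence, insufficient staple deployment, stapling without cutting, use of the manual retraction tool and others. Each reaches the primary endpoint only if a serious adverse event follows. If the surgeon rescues the situation without serious consequence, the event goes to the deficiency form and the descriptive secondary summary.

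At stake is what the study may conclude. It is meant for publication (Protocol 4.2), and its interim data are to support a regulatory submission (Protocol 13.6). A statement of confirmed performance that rests on passing the SADE limit could be challenged, because the plan names no performance result that would have prevented it.

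**Working it through.** **The plan's own figures.** Protocol 13.2 gives Poisson probabilities of observing adverse device effects (ADEs), with mean λ = 0.95 × n × rate.
- Abdominal: 0.95 × 53 × 0.033 = 1.662; 1 − exp(−1.662) = 81.0% (stated 81%).
- Thoracic: 0.95 × 74 × 0.025 = 1.758; 1 − exp(−1.758) = 82.8% (stated 83%).
- Combined: 0.95 × 127 × 0.029 = 3.499; at least one 97.0% (stated 97%); at least two, 1 − exp(−λ)(1 + λ) = 86.4% (stated 86%).

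All four reproduce. They concern ADEs; no malfunction rate enters them, and none is given anywhere in the documents.

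**What the criterion responds to.** The interval method is not named, so I assume Clopper-Pearson. The upper limit for x events in n subjects is the 97.5% quantile of Beta(x + 1, n − x). For x = 0 this is 1 − 0.025^(1/n).

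| Group | n | Upper limit at 0 SADEs | Most SADEs that still pass | First count that fails |
|---|---|---|---|---|
| Abdominal | 53 | 6.7% | 4 (18.2%) | 5 (20.7%) |
| Thoracic | 74 | 4.9% | 7 (18.5%) | 8 (20.2%) |
| Combined | 127 | 2.9% | 16 (19.7%) | 17 (20.6%) |

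After 5% attrition the largest passing counts are 4/50, 7/70 and 15/120. A Wilson interval would allow 8/74; a Wald interval would allow 6/53, 9/74 and 17/127. If the true SADE rate were as high as the planning rates for all ADEs, the exact rule at the enrolled n would be passed with probability 97.0% in the abdominal arm and above 99.9% in the thoracic arm and combined. The number of malfunctions without serious harm changes none of these figures.

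**What the secondary analysis would show.** The planned output is a count and a percentage. The malfunction counts below are assumptions over a range, with exact 95% limits: lower, the 2.5% quantile of Beta(x, n − x + 1); upper, as above.

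| Procedures with a malfunction, of 127 | Percentage | Exact 95% CI |
|---|---|---|
| 7 | 5.5% | 2.2% to 11.0% |
| 13 | 10.2% | 5.6% to 16.9% |
| 25 | 19.7% | 13.2% to 27.7% |
| 38 | 29.9% | 22.1% to 38.7% |

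In every row, with no SADEs, the sole criterion is met at 2.9%. The plan reports neither the interval nor any consequence for the conclusion.

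**Two gaps found by setting sections side by side.**
- SAP 7.9 lists the staple-line outcomes, infection and readmission, but not the malfunction types in Protocol 9.7.1, and it defines no numerator or denominator for malfunctions. SAP 7.10 tabulates adverse events only.
- Protocol 5.1.1 and 13.2 and SAP 4.1 and 6 include leaks in the primary endpoint. Protocol 13.4.1 and SAP 7.9 do not mention them. No section says whether a leak without serious consequence counts.

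**The case against.** The case on the other side has real content.

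- **No section declares performance confirmed on SADEs alone.** Protocol 13.4.1 confines the limit to its own endpoint, and 5.1 is an objective rather than a decision rule. The SAP does not repeat the 20% limit, and SAP 7.5 calls the primary analysis descriptive. This stands. A reader might infer that a poorly performing device would be declared confirmed; the documents support only that the wording leaves room for it.
- **Performance has its own data.** SAP 7.9 assesses the objectives through the endpoints and sets out both primary and secondary ones. Protocol 5.1.2 is about intended performance, and 9.7 uses deficiencies to assess efficacy. This stands too, so it would be too strong to say that the trial cannot fail on performance. But no section says how these data bear on the conclusion or what result would count against it.
- **The primary endpoint is not silent on performance.** Protocol 5.1.1 brings in leaks, and 11.1.3 counts harm from a malfunction, giving leaking or bleeding from non-functional staple closure as an example. A rescued malfunction may therefore qualify if its consequence is serious. So it would be wrong to say that the SADE rate tells us nothing about performance. It remains insensitive to failures without serious harm.
- **A descriptive secondary endpoint is legitimate** in a non-comparative post-market study, and a reader can compute an interval from a reported count and denominator. Agreed; no performance threshold is asked for here. The mismatch is between descriptive performance data and an objective worded as confirmation.

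**Conclusion.** The point holds as a mismatch between wording and decision rule. Serious adverse device effects are named as the means of confirming both safety and performance, and only that endpoint has a criterion. Malfunctions without serious harm cannot affect it: with no SADEs the exact upper limits are 6.7%, 4.9% and 2.9% (abdominal, thoracic, combined) at any malfunction count. Performance is measured, but without a criterion or an interval, so a claim of confirmed performance could be made that no malfunction result could overturn.

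The SADE figures assume exact intervals on the enrolled numbers; the zero-event conclusion does not depend on the malfunction rate. The malfunction counts in the working are illustrative, because the documents give none. This is a low-cost improvement to what the study can claim, not a flaw that invalidates its safety analysis.

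**What to change.** 1. In Protocol 5.1, the synopsis and SAP 4, state that the SADE criterion supports safety only, and that performance is described by the secondary endpoint.
2. In Protocol 13.4.2 and SAP 7.9, report the proportion of procedures with at least one device deficiency or malfunction, and each staple-line incidence, with a two-sided exact 95% confidence interval, by arm and combined.
3. Reconcile Protocol 5.1.1 and 13.2 and SAP 4.1 and 6 with Protocol 13.4.1 and SAP 7.9 on whether leaks, and in particular leaks without serious consequence, count in the primary endpoint.
4. A malfunction rate per firing is optional. The number of firings is already collected (Protocol 9.7.1), but firings cluster within subjects, so the interval would have to allow for that.

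The cost is some protocol and SAP wording and a few table columns. Items 1 and 2 need no new data or subjects, since deficiencies already go on a dedicated form. The downside for the sponsor is that the study could no longer say that meeting the SADE limit confirmed performance.
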